# Appendix B: International Myeloma Working Group Uniform Response Criteria

Response Category a	Response Criteria	
Stringent Complete Response (sCR)	Complete response (CR) as defined below, plus Normal serum free light chain (FLC) ratio and Absence of clonal plasma cells by immunohistochemistry or 2- to 4-color flow cytometry	
Complete Response (CR)	Negative immunofixation of serum and urine and Disappearance of any soft tissue plasmacytomas and ≤ 5% plasma cells in bone marrow  In patients in whom the only measurable disease is by serum FLC levels: CR in such patients indicates a normal FLC ratio of 0.26 to 1.65 in addition to CR criteria listed above.	
Very Good Partial Response (VGPR)	Serum and urine M-protein detectable by immunofixation but not on electrophoresis or 90% or greater reduction in serum M-protein plus urine M-protein level <100 mg per 24 hours  In patients in whom the only measurable disease is by serum FLC levels: VGPR in such patients requires a > 90% decrease in the difference between involved and uninvolved FLC levels.	
Partial Response (PR)	
 
≥ 50% reduction of serum M-Protein and reduction in 24-hour urinary M-protein by ≥ 90% or to < 200 mg per 24 hours
 
If the serum and urine M-protein are not measurable, a ≥ 50% decrease in the difference between involved and uninvolved FLC levels is required in place of the M-protein criteria.
 
If serum and urine M-protein are unmeasurable, and the serum free light chain assay is also unmeasurable, a ≥ 50% reduction in plasma cells is required in place of M-protein, provided baseline bone marrow plasma cell percentage was ≥ 30%
 
In addition to the above, if present at baseline a ≥ 50% reduction in the size of soft tissue plasmacytomas is also required.
 
	
Stable Disease (SD)	Not meeting criteria for CR, VGPR, PR, or progressive disease (PD)	

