# 1.2. Compound Background

# **1.2.1. Durvalumab (MEDI4736)**

Durvalumab (MEDI4736; DURVA) is a human immunoglobulin (Ig) G1 kappa monoclonal antibody (mAb) directed against human programmed death ligand-1 (PD-L1) protein. Durvalumab is expressed in Chinese hamster ovary cells and has an overall molecular weight of approximately 149 kDa. Durvalumab selectively binds human PD-L1 with high affinity and blocks its ability to bind to programmed cell death 1 (PD-1) protein and cluster of differentiation (CD)80. The fragment crystallizable (Fc) domain of DURVA contains a triple mutation in the constant domain of the IgG1 heavy chain that reduces binding to the complement component C1q and the Fc gamma receptors responsible for mediating antibody-dependent cell-mediated cytotoxicity (ADCC) (Oganesyan, 2008).

[figure not shown]

Figure 1: Mechanism of Action for Durvalumab

[figure not shown]
Refer to the DURVA Investigator's Brochure (IB) for detailed information concerning the available pharmacology, toxicology, drug metabolism, clinical studies, and adverse event (AE) profile of the investigational product (IP).

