#### 1.2.2. Daratumumab

Daratumumab (DARA) is a human IgG1k monoclonal antibody that binds with high affinity to a unique epitope on CD38. It is a targeted immunotherapy that attacks tumor cells that overexpress CD38, a transmembrane glycoprotein, in a variety of hematological malignancies including multiple myeloma. Daratumumab was approved under the accelerated approval regulations in the United States (US) on 16 November 2015, and in the European Union (EU) on 24 May 2016, for the treatment of patients with multiple myeloma who have received at least three prior lines of therapy including a proteasome inhibitor (PI) and an immunomodulatory agent or who are double-refractory to a PI and an immunomodulatory agent.

Daratumumab induces tumor cell death through diverse mechanisms of action, which include complement-dependent cytotoxicity (CDC), antibody dependent cell-mediated cytotoxicity (ADCC), antibody-dependent cellular phagocytosis, and induction of apoptosis (de Weers, 2011; Lammerts van Bueren, 2014; Overdijk, 2015; Jansen 2012).

Figure 2: Mechanisms of Daratumumab Activity

DARA, daratumumab; MM, multiple myeloma; CDC, complement dependent cytotoxicity; ADPC, antibody-dependent cellular phagocytosis; ADCC, antibody-dependent cell-mediated cytotoxicity; NAD, nicotinamide adenine dinucleotide; Ca, calcium ion; MDSC, myeloid-derived suppressor cell; Breg, regulatory B cell; Treg, regulatory T cell; cADPR, cyclic adenosine diphosphate-ribose; NAADP, nicotinic acid adenine dinucleotide phosphate; AMP, adenosine monophosphate.

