# 6.4.2. Bone Marrow Aspiration and/or Biopsy

A bone marrow aspirate (BMA) and biopsy (BMB) is mandatory at the following time points:

- At screening, BMA and BMB for percent plasma cells, cytogenetics,
- During treatment:
  - \_ CCI
  - BMA and BMB at the time of complete response (CR) confirmation for percent plasma cells
  - \_ CCI

The analysis of bone marrow for percentage of plasma cells will be performed locally and at a central laboratory.

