# 6.8. Blood Type, Rh and Indirect Antiglobulin Test (IAT)

Blood type, Rh, and IAT should be done before the first dose of DARA for the reasons detailed below. Subject RBC phenotyping (standard or extended) is an alternative option to the IAT test, if locally required. Either method must be completed prior to first DARA infusion.

DARA interferes with the indirect antiglobulin test (IAT), which is a routine pre-transfusion test performed to identify a patient's antibodies to minor antigens so that suitable donor blood can be given for transfusion. DARA does not interfere with ABO/RhD typing. CD38 is expressed at very low levels on erythrocytes. DARA binds to the CD38 on erythrocytes, which results in a

positive IAT (Indirect Coombs Test). This positive result masks the detection of antibodies to minor antigens and may prevent or delay blood banks from issuing donor blood for transfusion. This effect occurs during DARA treatment and for up to 6 months after treatment ends. Subjects will receive a patient identification wallet card for the study that includes the blood profile (ABO, Rh, and IAT or phenotyping) determined before the first infusion of DARA along with information on the IAT interference for healthcare providers/blood banks. Subjects are to carry this card throughout the treatment period and for at least 6 months after treatment ends. Blood banks can eliminate the DARA interference with IAT by treating reagent RBCs with dithiothreitol (DTT) (Chapuy, 2015).

Possible methods for blood banks to provide safe RBCs for transfusion to subjects receiving DARA include:

- a. Providing ABO/RhD compatible, phenotypically (standard or extended phenotyping) or genotypically matched units
- b. Providing ABO/RhD compatible, K-negative units after ruling out or identifying alloantibodies using dithiothreital-treated reagent RBCs

Uncrossmatched, ABO/RhD compatible RBC units should be administered if transfusion is needed emergently as per local blood bank practice.

Despite DARA binding to CD38 on erythrocytes, no indication of clinically significant hemolysis has been observed in DARA studies. For additional details, refer to the DARA IB.

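### CR and sCR can be under-called as VGPR, because negative immunofixation is required while two infused IgG1-kappa antibodies are on board and no written rule sets a drug band aside.

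*Protocol*

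**What the plan says.** Protocol Appendix B opens the CR definition with "Negative immunofixation of serum and urine". It defines sCR as "Complete response (CR) as defined below" plus further conditions, so a missed CR is also a missed sCR. The first route to VGPR is "Serum and urine M-protein detectable by immunofixation but not on electrophoresis". SAP Table 6 repeats these criteria. The footnote to both tables asks for two consecutive assessments.

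Protocol Section 1.2.1 says that durvalumab "is a human immunoglobulin (Ig) G1 kappa monoclonal antibody (mAb"), and Section 1.2.2 that daratumumab "is a human IgG1 k monoclonal antibody". Section 6.4.1 schedules serum and urine immunofixation at screening, on Day 1 of each cycle and at end of treatment. Section 6.2 places evaluations before dosing on the visit day.

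The one assay interference that the visible text handles is in Section 6.8: "DARA interferes with the indirect antiglobulin test (IAT"). Section 6.4.2 requires "BMA and BMB at the time of complete response (CR) confirmation for percent plasma cells".

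Protocol Section 9.6.1 and SAP Section 10.1 tabulate the proportion in each IMWG category beside the ORR, with exact 95% confidence intervals.

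**The concern.** Immunofixation types a monoclonal band by its heavy and light chain. An infused IgG-kappa antibody still circulating at sampling can appear as an IgG-kappa band, and nothing in the CR definition allows the reader to set it aside. Daratumumab already present at baseline does not cancel out, because CR is an absolute criterion and not a change from baseline.

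The error runs one way: the drugs can hide a CR but cannot create one. What is at stake is the CR and sCR rows, and the VGPR row that absorbs the missed cases. There may be a knock-on effect. The marrow for percent plasma cells is tied to CR confirmation, so if CR is never suspected that sample may not be taken, and later re-adjudication could not recover the category. This is an inference, since other on-treatment marrow entries in Section 6.4.2 are redacted.

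**Working it through.** **1. The plan's own figures, and whether they move.** Inputs from Protocol Section 9.3: at least 3 of 18 to continue, at least 9 of 50 to reject, null 10%, target 25%. The probability of rejecting is the sum over x = 3 to 18 of P(Bin(18, p) = x) × P(Bin(32, p) ≥ 9 − x).

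- p = 0.10: 0.0437, within the stated 0.05.
- p = 0.25: 0.818, meeting the stated 80%.

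The event counted is PR or better. A subject who misses CR only on immunofixation falls to VGPR and remains a responder, so neither figure changes. TTR and DOR start at PR or better. PFS ends at PD or death, and the PD criteria in Appendix B do not use immunofixation.

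**2. Is a band plausible at the time of sampling?** Samples are pre-dose, so trough levels matter and not the level just after infusion. From the documents: DARA 16 mg/kg, DURVA 1500 mg, and dosing intervals of 7, 14 or 28 days. Assumed, because the documents do not give them: 70 kg body weight, volume 3-6 L, half-life h of 7-21 days, steady state.

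Rise per dose, C0 = dose / volume:
- DARA: 16 × 70 = 1120 mg over 3-6 L = 0.0187-0.0373 g/dL.
- DURVA: 1500 mg over 3-6 L = 0.025-0.050 g/dL.

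Trough = C0 × r / (1 − r), with r = 2^(−interval/h).

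| Drug and interval | r/(1 − r), h = 7 to 21 days | Trough, g/dL |
|---|---|---|
| DARA QW | 1.00 to 3.85 | 0.019-0.144 |
| DARA Q2W | 0.333 to 1.70 | 0.006-0.064 |
| DARA Q4W | 0.067 to 0.658 | 0.001-0.025 |
| DURVA every 28 days | 0.067 to 0.658 | 0.002-0.033 |

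The documents give no detection limit for immunofixation. Against an assumed 0.01-0.03 g/dL, a pre-dose band is likely on QW DARA, and possible but not certain on Q4W DARA plus DURVA. Q2W lies between. Under Protocol Table 3, QW dosing covers Weeks 1 to 8 before moving to Q2W in subjects with SD or better, so the clearest exposure is early.

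**3. How many subjects could be misclassified?** Only those who would otherwise reach CR. The IgG-kappa share is not in the documents; take 20-40%, and suppose that every IgG-kappa CR is lost.

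- Assumed CR rate 10%: 50 × 0.10 = 5 true CRs; 5 × 0.20 to 0.40 = 1-2 subjects.
- Every responder at the 25% target ORR a CR: 50 × 0.25 = 12.5; 12.5 × 0.20 to 0.40 = 2.5-5 subjects.

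These counts cover IgG-kappa subjects. If 'negative' were also enforced literally in other types, and a drug band were always visible, the rest of the 5 (or 12.5) would be exposed too. There, however, a reader can see that the band is not of the subject's own type.

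**The case against.** The strongest reply is that nothing the trial decides depends on CR. ORR is PR or better, CR rate is not a named endpoint in the visible rows of Protocol Table 2 or SAP Table 3, and SAP Section 10 calls all efficacy analyses descriptive. Testing is central, and myeloma experts adjudicate under an IRAC charter that is not among the documents; a rule on therapeutic bands could well be there. Subjects may start on Q4W DARA, where pre-dose levels may lie below detection.

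All of this stands, and it limits severity and certainty. It does not remove the gap. Investigators assess response from Appendix B (Section 6.4.5.1), and the IRAC is told to use the same criteria (Section 6.4.5.2). As written, those criteria can give the wrong label in rows that the plan does report.

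Three stronger readings are tempting and not supported:

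- A reader might apply the 20-40% share to all 50 subjects and conclude that 10-20 cannot be called CR. That counts subjects who would never have reached CR.
- A reader might compare the drug level just after infusion with 10% of the 0.5 g/dL entry threshold, which is 0.05 g/dL. Sampling is pre-dose, and a 90% fall is a VGPR criterion; CR has no percentage threshold.
- A reader might take Section 6.8 as an admission that immunofixation is affected. That section describes binding to CD38 on red cells, a different mechanism. It shows only that assay interference was considered in one place.

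**Conclusion.** The point holds in a limited form: CR and sCR **can be** under-called as VGPR. That they are under-called, or by how much, cannot be shown from the documents, because trough levels, the assay limit and the IgG-kappa share are all missing. On the assumptions above, the loss among IgG-kappa subjects is about 1-2 of 50 at a 10% CR rate, and 2.5-5 of 50 at the target ORR if every responder were a CR.

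A reader might also infer that the primary result is biased downwards. It is not, through this criterion: ORR, the 3-of-18 and 9-of-50 rules, TTR, DOR and PFS are the same whether the subject is labelled CR or VGPR. Severity is minor and confined to the descriptive depth-of-response rows. A rule in the IRAC charter, if it exists, would reduce the point to aligning Appendix B and SAP Table 6 with it.

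**What to change.** 1. In Appendix B, SAP Table 6 and the IRAC charter, state that an IgG-kappa band in a subject whose baseline M-protein is of another type does not by itself prevent CR. The sentence needs to be in force during the trial, so that the marrow already planned at CR confirmation is taken.
2. Keep IgG-kappa subjects who miss CR only on an IgG-kappa immunofixation band in the IMWG VGPR row, with a flag: *CR not assessable on study antibodies*. This adds no new response category.
3. Tabulate CR and sCR by baseline type, IgG-kappa against other. Take the type from the quantifiable baseline M-protein, the involved free light chain or the known myeloma subtype. Do not rely on screening immunofixation alone: subjects have progressed on DARA as their last therapy (inclusion criterion 2) and DARA is exempt from the washout (exclusion criteria 4 and 5), so a DARA band may already be present.

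The cost is wording in three documents and one split table, with no new type of sample and no change to the primary analysis. The downside is that CR stays undetermined in some IgG-kappa subjects; the flag shows this openly and does not count them silently as having missed CR.

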# **Appendix B: International Myeloma Working Group Uniform Response Criteria (Continued)**

Response Category a	Response Criteria	
Progressive disease (PD)	Requires only one of the following:	
	Increase of 25% from lowest response value in any of the following:	
	
 
Serum M-component (absolute increase must be ≥ 0.5 g/dL), and/or
 
	
	
 
Urine M-component (absolute increase must be ≥ 200 mg/24 h), and/or
 
	
	Only in patients without measurable serum and urine M-protein levels: the difference between involved and uninvolved FLC levels (absolute increase must be $\geq 10$ mg/dL)	
	Only in patients without measurable serum and urine M protein levels and without measurable disease by FLC levels, bone marrow plasma cell percentage (absolute percentage must be $\geq 10\%$ )	
	Definite development of new bone lesions or soft tissue plasmacytomas or definite increase in the size of existing bone lesions or soft tissue plasmacytomas	
	Development of hypercalcemia (corrected serum calcium > 11.5 mg/dL) that can be attributed solely to the plasma cell proliferative disorder	
Additional Response Crite	eria	
Molecular Complete Response	CR plus negative allele-specific oligonucleotide polymerase chain reaction (ASO-PCR), sensitivity 10 	
Immunophenotypic	Stringent CR plus	
Complete Response	Absence of phenotypically aberrant plasma cells (clonal) in bone marrow (BM) with a minimum of 1 million total BM cells analyzed by multiparametric flow cytometry (with > 4 colors)	
Minimal Response (MR)	≥ 25% but ≤ 49% reduction of serum M-protein and reduction in 24-hour	
in patients with relapsed	urine M-protein by 50%-89%	
refractory myeloma adopted from the European	In addition to the above criteria, if present at baseline, 25%-49% reduction in the size of soft tissue plasmacytomas is also required	
Group for Blood and	No increase in size or number of lytic bone lesions (development of	
Marrow Transplantation (EBMT) criteria	compression fracture does not exclude response)	

<sup>a All response categories (CR, sCR, VGPR, PR, and PD) require 2 consecutive assessments made at any time before the institution of any new therapy; CR, sCR, VGPR, PR, and SD categories also require no known evidence of progressive or new bone lesions if radiographic studies were performed. VGPR and CR categories require serum and urine studies regardless of whether disease at baseline was measurable on serum, urine, both, or neither. Radiographic studies are not required to satisfy these response requirements. Bone marrow assessments need not be confirmed. For PD, serum M-component increases of more than or equal to 1 g/dL are sufficient to define relapse if the starting M-component is ≥ 5 g/dL.

# **Appendix C: ECOG Performance Status**

### Eastern Cooperative Oncology Group (ECOG) Performance Status

Grade	ECOG Performance Status		
0	Fully active, able to carry on all pre-disease performance without restriction		
1	Restricted in physically strenuous activity but ambulatory and able to carry out work of a light or sedentary nature, eg, light house work, office work		
2	Ambulatory and capable of all self-care but unable to carry out any work activities. Up and about more than 50% of waking hours		
3	Capable of only limited self-care, confined to bed or chair more than 50% of waking hours		
4	Completely disabled. Cannot carry on any self-care. Totally confined to bed or chair		
5	Dead		

Eastern Cooperative Oncology Group, [name], Group Chair

# Appendix D: Staging Systems for Multiple Myeloma

**Table 11:** Staging Systems for Multiple Myeloma

Stage	Durie-Salmon Criteria a	International Staging System (ISS) Criteria
I	All of the following:  Hemoglobin value > 10 g/dL  Serum calcium value normal or < 12 mg/dL  Bone x-ray, normal bone structure (scale 0), or solitary bone plasmacytoma only  Low M-component production rates  IgG value < 5 g/dL;  IgA value < 3 g/dL  Urine light chain M-component on	Serum beta-2 microglobulin < 3.5 mg/L Serum albumin ≥ 3.5 g/dL
II	electrophoresis < 4 g/24h  Neither Stage I nor Stage II	Neither Stage I nor Stage II
III	One or more of the following:  Hemoglobin value < 8.5 g/dL  Serum calcium value normal or > 12 mg/dL  Advanced lytic bone lesions (scale 3)  High M-component production rates  IgG value > 7 g/dL;  IgA value > 5 g/dL  Urine light chain M-component on electrophoresis > 12 g/24h	Serum beta-2 microglobulin ≥ 5.5 mg/L
Subclassification Criteria  A Normal renal function (serum creatinine value $< 2.0$ mg/dL)  B Abnormal renal function (serum creatinine value $\ge 2.0$ mg/dL)		Not applicable

<sup>a Durie, 1975.

<sup>b Greipp, 2005.

# Appendix E: Durvalumab Treatment Modification and Toxicity Management Guidelines

Note: The toxicity management guidelines in Appendix E-1, E-2, and E-3 prepared by the Sponsor are to assist the investigator in the exercise of his/her clinical judgment in treating these types of toxicities and should be applied to management of adverse events related to study treatment and not ANY adverse event.

Appendix E-1: Durvalumab Treatment Modification and Toxicity Management Guidelines for Immune-related Adverse Events

	Immune-Mediated Reaction	ons
	Dose Modifications	Toxicity Management
Immune-related Adverse Events (Overall Management For toxicities not noted below)	Drug administration modifications of study drug/study regimen will be made to manage potential immune-related AEs based on severity of treatment-emergent toxicities graded per NCI CTCAE v4.03.  In addition to the criteria for permanent discontinuation of study drug/regimen based on CTC grade/severity (table below), permanently discontinue study drug/study regimen for the following conditions:  • Inability to reduce corticosteroid to a dose of ≤10 mg of prednisone per day (or equivalent) within 12 weeks after last	It is recommended that management of irAEs follow the guidelines presented in this table  - Patients should be thoroughly evaluated to rule out any alternative etiology (eg, disease progression, concomitant medications, infections, etc.)  - In the absence of a clear alternative etiology, all events should be considered potentially immune related.  - Symptomatic and topical therapy should be considered for low-grade (Grade 1 or 2, unless otherwise specified) events
	
 
dose of study drug/regimen
 
Recurrence of a previously experienced Grade 3 treatment-related AE following resumption of dosing.
 
Grade 1 No dose modification
 
Grade 2 Hold study drug/study regimen dose until Grade 2 resolution to ≤ Grade 1
 
If toxicity worsens then treat as Grade 3 or
 
	
 
For persistent (greater than 3 to 5 days) low-grade (Grade 2) or severe (Grade ≥3) events promptly start prednisone PO 1-2mg/kg/day PO or IV equivalent
 
If symptoms recur or worsen during corticosteroid tapering 28 days of taper), increase the corticosteroid dose (prednisone dose [eg, up to 2-4mg/kg/day PO or IV equivalent]) until stabilization or improvement of symptoms, then resume corticosteroid tapering at a slower rate (≥ 28 days of taper)
 

	Grade 4  Study drug/study treatment can be resumed at the next scheduled dose once event stabilizes to Grade ≤1 after completion of steroid taper  Patients with endocrinopathies who may require prolonged or continued steroid replacement	
 
More potent immunosuppressives such as TNF inhibitors (eg, infliximab) – (also refer to the individual sections of the immune related adverse event for specific type of immunosuppressive) should be considered for events not responding to systemic
 

Immune-Mediated Reaction			ns
		Dose Modifications	Toxicity Management
		can be retreated with study drug/study regimen on the following conditions: 1) the event stabilizes and is controlled, 2) the patient is clinically stable as per Investigator or treating physician's clinical judgement, and 3) doses of prednisone are at less than or equal to 10 mg/day or equivalent.	steroids.  - Discontinuation of study drug is not mandated for Grade 3 / Grade 4 inflammatory reactions attributed to local tumour response (eg, inflammatory reaction at sites of metastatic disease, lymph nodes etc.).  Continuation of study drug in this situation should be based upon a benefit/risk analysis for that patient
	po	epending on the individual toxicity, may ermanently discontinue study drug/study egimen. Please refer to guidelines below	
		ermanently discontinue study drug/study	
	hold study drug/regin	nd above asymptomatic amylase or lipase levels nen and if complete work up shows no evidence ontinue or resume study drug/regimen	
Pneumonitis/ILD	Grade of Pneumonitis (CTCAE version 4.03)	General Guidance	
 
Monitor patients for signs and symptoms of pneumonitis or ILD (new onset or worsening shortness of breath or cough). Patients should be evaluated with imaging and pulmonary function tests including other diagnostic procedures as described below
 

		bP-0	
 
Initial work-up may include clinical evaluation, monitoring of oxygenation via pulse oximetry (resting and exertion), laboratory work-up and high-resolution CT scan.
 

	Grade 1 (Asymptomatic, clinical or diagnostic observations only, intervention not indicated)	No dose modification required. However, consider holding study drug/study regimen dosing as clinically appropriate and during diagnostic work-up for other etiologies	For Grade 1 (Radiographic Changes Only)  - Monitor and closely follow up in 2-4 days for clinical symptoms, pulse oximetry (resting and exertion) and laboratory work-up and then as clinically indicated  - Consider pulmonary and infectious disease consult

	Immune-Mediated Reaction	ons
	Dose Modifications	Toxicity Management
Grade 2 (Symptomatic, medical intervention indicated, limiting instrumental ADL)	
 
Hold study drug/study regimen dose until Grade 2 resolution to ≤ Grade 1
 
If toxicity worsens then treat as Grade 3 or Grade 4
 
If toxicity improves to ≤ Grade 1 then the decision to reinitiate study drug/regimen will be based upon treating physician's clinical judgment and after completion of steroid taper.
 
	
 
For Grade 2 (Mild to Moderate New Symptoms)
 
Monitor symptoms daily and consider hospitalization
 
Promptly start systemic steroids (eg, prednisone 1-2mg/kg/day PO or IV equivalent)
 
Reimaging as clinically indicated
 
If no improvement within 3-5 days, additional workup should be considered and prompt treatment with IV methylprednisolone 2-4mg/kg/day started
 
If still no improvement within 3-5 days despite IV methylprednisone at 2-4/g/kg/day, promptly start immunosuppressive therapy such as TNF inhibitors (eg, infliximab at 5 mg/kg every 2 weeks). Caution: Important to rule out sepsis and refer to infliximab label for general guidance before using infliximab
 
Once improving, gradually taper steroids over ≥ 28 days and consider prophylactic antibiotics, antifungal or anti PCP treatment (refer to current NCCN guidelines for treatment of cancer-related infections (Category 2B recommendation)
 
Consider pulmonary and infectious disease consult
 
Consider as necessary discussing with study physician
 

Grade 3 or 4 (Grade 3: Severe symptoms; limiting self-care ADL; oxygen indicated;  Grade 4: life threatening respiratory compromise, urgent intervention	Permanently discontinue study drug/study regimen	For Grade 3 or 4 (severe or new symptoms, new/worsening hypoxia, life threatening  - Promptly initiate empiric IV methylprednisolone 1 to 4 mg/kg/day or equivalent  - Obtain pulmonary and infectious disease consult  - Hospitalize the patient  - Supportive Care (oxygen, etc.)  - If no improvement within 3-5 days, additional workup should be considered and prompt treatment with

Immune-Mediated Reactions			
		Dose Modifications	Toxicity Management
	indicated [eg, tracheostomy or intubation])		additional immunosuppressive therapy such as TNF inhibitors (eg, infliximab at 5 mg/kg every 2 weeks dose) started. Caution: rule out sepsis and refer to infliximab label for general guidance before using infliximab  - Once improving, gradually taper steroids over ≥28 days and consider prophylactic antibiotics, antifungals and in particular, anti PCP treatment (please refer to current NCCN guidelines for treatment of cancer-related infections (Category 2B recommendation) a
Diarrhea/ Enterocolitis	Grade of Diarrhea (CTCAE version 4.03)	General Guidance	
 
Monitor for symptoms that may be related to diarrhea/enterocolitis (abdominal pain, cramping, or changes in bowel habits such as increased frequency over baseline or blood in stool) or related to bowel perforation (such as sepsis, peritoneal signs and ileus)
 
Patients should be thoroughly evaluated to rule out any alternative etiology (eg, disease progression, other medications, infections including testing for clostridium difficile toxin, etc.)
 
Steroids should be considered in the absence of clear alternative etiology, even for low grade events, in order to prevent potential progression to higher grade event
 
Use analgesics carefully; they can mask symptoms of perforation and peritonitis
 

	Grade 1 diarrhea (stool frequency of <4 over baseline per day)	No dose modification	For Grade 1 diarrhea:  - Close monitoring for worsening symptoms  - Consider symptomatic treatment including hydration, electrolyte replacement, dietary changes (eg, American Dietetic Association colitis diet), and loperamide. Use of probiotics as per treating physician's clinical judgment.
	Grade 2 diarrhea (stool frequency of	Hold study drug/study regimen until resolution to ≤ Grade 1	For Grade 2 diarrhea:  - Consider symptomatic treatment including hydration,

EDMS Doc. Number: CCI

	Immune-Mediated Reactio	ns
	Dose Modifications	Toxicity Management
4-6 over baseline per day)	
 
If toxicity worsens then treat as Grade 3 or Grade 4
 
If toxicity improves to ≤ Grade 1 then study drug/study regimen can be resumed after completion of steroid taper
 
	electrolyte replacement, dietary changes (eg, American Dietetic Association colitis diet), and loperamide and/or budesonide  Promptly start prednisone 1 to 2 mg/kg/day PO or IV equivalent  If event is not responsive within 3-5 days or worsens despite prednisone at 1-2 mg/kg/day PO or IV equivalent, GI consult should be obtained for consideration of further workup such as imaging and/or colonoscopy to confirm colitis and rule out perforation, and prompt treatment with IV methylprednisolone 2-4mg/kg/day started.  If still no improvement within 3-5 days despite 2-4mg/kg IV methylprednisolone, promptly start immunosuppressives such as (infliximab at 5 mg/kg once every 2 weeks³). Caution: Important to rule out bowel perforation and refer to infliximab label for general guidance before using infliximab  Consult study physician if no resolution to ≤ Grade 1 in 3-4 days  Once improving, gradually taper steroids over ≥28 days and consider prophylactic antibiotics, antifungals and anti PCP treatment (please refer to current NCCN guidelines for treatment of cancer-related infections [Category 2B recommendation])

<sup>3 ASCO Educational Book 2015 Michael Postow MD "Managing Immune Checkpoint Blocking Antibody Side Effects.

Immune-Mediated Reactions			
	Dose Modifications		Toxicity Management
	Grade 3 or 4 diarrhea  (Grade 3: stool frequency of ≥7 over baseline per day;  Grade 4: life threatening consequences)	Permanently discontinue study drug/study regimen	For Grade 3 or 4 diarrhea:  - Promptly initiate empiric IV methylprednisolone 2 to 4 mg/kg/day or equivalent  - Monitor stool frequency and volume and maintain hydration  - Urgent GI consult and imaging and/or colonoscopy as appropriate  - If still no improvement within 3-5 days of IV methylprednisolone 2 to 4mg/kg/day or equivalent, promptly start further immunosuppressives (eg, infliximab at 5 mg/kg once every 2 weeks).  - Caution: Ensure GI consult to rule out bowel
			perforation and refer to infliximab label for general guidance before using infliximab.  - Once improving, gradually taper steroids over ≥28 days and consider prophylactic antibiotics, antifungals and anti PCP treatment (please refer to current NCCN guidelines for treatment of cancer-related infections [Category 2B recommendation])
Hepatitis (Elevated LFTs)  Infliximab should not be	Grade of Liver Function Test Elevation (CTCAE version 4.03) Any Grade	opoly,	
 
Monitor and evaluate liver function test: AST, ALT, ALP and total bilirubin
 
Evaluate for alternative etiologies (eg, viral hepatitis, disease progression, concomitant medications)
 

used for management of Immune Related Hepatitis	Grade 1 (AST or ALT > to 3 times ULN and/or TB > to 1.5 times ULN)	No dose modification If it worsens, treat as Grade 2 event	For Grade 1 AST or ALT and/or TB elevation  - Continue LFT monitoring per protocol

Immune-Mediated Reactions			
	Dose Modifications	Toxicity Management	
Grade 2 (AST or ALT > to 5 times ULN and/or TB > 1.5-times ULN)	• If toxicity worsens then treat as Grade 3 or	
 
For Grade 2 AST or ALT and or TB elevation:         
 
Regular and frequent checking of LFTs (eg, every 1-2 days) until elevations of these are improving or resolved.
 
If no resolution to ≤ Grade 1 in 1-2 days, discuss with study physician.
 
If event is persistent (> 3-5 days) or worsens, promptly start prednisone 1-2mg/kg/day PO or IV equivalent.
 
If still no improvement within 3-5 days despite 1-2mg/kg/day of prednisone PO or IV equivalent, consider additional workup and prompt treatment with IV methylprednisolone 2-4mg/kg/day started.
 
If still no improvement within 3-5 days despite 2-4mg/kg/day of IV methylprednisolone, promptly start immunosuppressives (mycophenolate mofetil).
 
Discuss with study physician if mycophenolate mofetil is not available. Infliximab should NOT be used.
 
Once improving, gradually taper steroids over ≥28 days and consider prophylactic antibiotics, antifungals and anti PCP treatment (please refer to current NCCN guidelines for treatment of cancer-related infections [Category 2B recommendation])
 
 
 
	
Grade 3 (AST or ALT > 20 times ULN and/or TB > 3.0-times ULN	-Hold study drug/study regimen dose until	For Grade 3 or 4 AST or ALT and/or TB elevation:  - Promptly initiate empiric IV methylprednisolone at 1 to 4 mg/kg/day or equivalent  - If still no improvement within 3-5 days despite 1 to 4 mg/kg/day methylprednisolone IV or equivalent,	

<sup>4 ASCO Educational Book 2015 "Managing Immune Checkpoint Blocking Antibody Side Effects", by Michael Postow MD.

Immune-Mediated Reactions			ns
		Dose Modifications	Toxicity Management
	Grade 4 (AST or ALT > 20 times ULN and/or TB > 10 times ULN)	baseline within 14 days and after completion with steroid taper.  Permanently discontinue study drug/study regimen if the elevations do not downgrade to ≤ Grade 1 or baseline within 14 days  For elevations in transaminases > 8 × ULN or elevations in bilirubin > 5 × ULN, discontinue study drug/study regimen  Permanently discontinue study drug/study regimen for any case meeting Hy's law criteria (AST and/or ALT > 3x ULN + bilirubin > 2x ULN without initial findings of cholestasis (ie, elevated alkaline P04) and in the absence of any alternative causeiv Permanently discontinue study drug/study regimen	
 
promptly start treatment with immunosuppressive therapy (mycophenolate mofetil) Discuss with study physician if mycophenolate is not available. Infliximab should NOT be used.
 
Hepatology consult, abdominal workup, and imaging as appropriate.
 
Once improving, gradually taper steroids over ≥28 days and consider prophylactic antibiotics, antifungals and anti PCP treatment (please refer to current NCCN guidelines for treatment of cancer-related infections [Category 2B recommendation])
 

Nephritis or Renal Dysfunction (Elevated Serum Creatinine)	Grade of Elevated Serum Creatinine (CTCAE version 4.03)  Any Grade	General Guidance	
 
Consult with Nephrologist
 
Monitor for signs and symptoms that may be related to changes in renal function (eg, routine urinalysis, elevated serum BUN and creatinine, decreased creatinine clearance, electrolyte imbalance, decrease in urine output, proteinuria, etc.)
 
Patients should be thoroughly evaluated to rule out any alternative etiology (eg, disease progression, infections etc.)
 
Steroids should be considered in the absence of clear alternative etiology even for low grade events (Grade 2), in order to prevent potential progression to higher grade event
 

Immune-Mediated Reactions		
	Dose Modifications	Toxicity Management
Grade 1 [Serum Creatinine > 1-1.5 X baseline; > ULN to 1.5 X ULN]	No dose modification	For Grade 1 elevated creatinine:  - Monitor serum creatinine weekly and any accompanying symptom  • If creatinine returns to baseline, resume its regular monitoring per study protocol.  • If it worsens, depending on the severity, treat as Grade 2 or Grade 3 or 4  - Consider symptomatic treatment including hydration, electrolyte replacement, diuretics, etc.
Grade 2 [Serum Creatinine>1.5-3.0 X baseline; >1.5 X- 3.0 X ULN]	
 
Hold study drug/study regimen until resolution to ≤ Grade 1 or baseline
 
If toxicity worsens then treat as Grade 3 or Grade 4
 
If toxicity improves to ≤ Grade 1 or baseline then resume study drug/study regimen after completion of steroid taper.
 
	
 
For Grade 2 elevated creatinine:         
 
Consider symptomatic treatment including hydration, electrolyte replacement, diuretics, etc.
 
Carefully monitor serum creatinine every 2-3 days and as clinically warranted
 
Consult Nephrologist and consider renal biopsy if clinically indicated
 
If event is persistent (> 3-5 days) or worsens, promptly start prednisone 1 to 2 mg/kg/day PO or IV equivalent
 
If event is not responsive within 3-5 days or worsens despite prednisone at 1-2 mg/kg/day PO or IV equivalent, additional workup should be considered and prompt treatment with IV methylprednisolone at 2-4mg/kg/day started.
 
Once improving gradually taper steroids over ≥28 days and consider prophylactic antibiotics, antifungals and anti PCP treatment (please refer to current NCCN guidelines for treatment of cancer-related infections [Category 2B recommendation]).
 
When event returns to baseline, resume study drug/study regimen and routine serum creatinine monitoring per study protocol.
 
 
 

		Immune-Mediated Reaction	ons
		Dose Modifications	Toxicity Management
